**Table 2. Screening assessments**

Inclusion/Exclusion assessments	Safety assessments
-Hemoglobin A1c $\geq$ 7.5% -Pregnancy clinical criteria with pregnancy testing as indicated (in females age 55 years old or younger) -Perceived Stress Scale-10 score $\geq$ 12	-PHQ-9 -modified P4 Screener if 9 th item of PHQ-9 is 1 or greater -MINI structured interview

Overview of Study Visit Time Windows (See Table 3): The screening visit will be scheduled within 10 weeks and 2 days (72 days) before the start of the study intervention (Orientation session). The baseline study visit will be scheduled within 6 weeks and 2 days (44 days) before the Orientation session (to allow for sufficient time for scheduling around holidays). Randomization will take place during the week before the Orientation session. Class #1 (the first class after Orientation) will start ~1 week after the Orientation session. The follow-up phone call will be scheduled within the 2 weeks after Class #4. The 2-month study visit will be scheduled within the 4 weeks immediately after Class #8 (the end of the 8-week MBSR or SME program). The 6-month study visit will be scheduled within the 4 weeks immediately after Booster session #4. The time windows for capturing the optional 24-hour diet recall data are within 2 weeks before Class #1, 2 weeks after Class #8, and 2 weeks before Booster #4. The time windows for capturing the optional Actigraph data are +/- 2 weeks of the baseline and 2-month study visits, and in the 4 weeks before the 6-month study visit.

It is possible that a subject completes the screening visit, or the screening and baseline visits, for a cohort and then is unable to be randomized to that cohort and needs to wait to be

randomized to a later cohort (due to reaching the maximum number of participants permitted in a class, or due to the subject not being reached in time for randomization, or due to the subject requesting to participate in a later cohort when they will be more available). In these scenarios, the screening and baseline visits will need to be repeated if they fall outside of the Study Visit Windows for the new later cohort. In other words, the screening visit will need to be repeated if it is more than 10 weeks and 2 days (72 days) before the new later Orientation session, and the baseline visit will need to be repeated if it is more than 6 weeks before the new later Orientation session. Subjects will need to attend the screening visit and baseline visit within the specified time window in order to be randomized. In these instances, all data from screens and visits that were collected during times when the subject was not randomized will be maintained. However, only the screening and baseline data provided by the subject within the specified time windows will be used in analysis. Data collected from earlier duplicate screens will be maintained and documented securely in REDCap, therefore it is possible that multiple study ID numbers correspond to one randomized subject.

The research coordinator will make 3 attempts to reach a subject for the follow-up phone call within the 2 weeks after Class #4. If a subject misses the follow-up phone call within this specified 2-week time window, the subject will not be withdrawn from the study, and their follow-up phone call data will be considered missing data. If a subject misses the 2-month study visit within the specified time window, the research coordinator will contact them and if the subject confirms that they are willing to come in for the final 6-month study visit, the subject will not be withdrawn from the study and their 2-month study visit data will be considered missing data.

**Lost to Follow-up:** Subjects will be withdrawn from the study and considered lost to follow-up if they cannot be reached after doing the following:

- First, the research coordinator will call and e-mail the subject once a week for 3 weeks.
- If no response, then the research coordinator will make 3 attempts to call their emergency contact if they provided an emergency contact. Subjects will be asked to provide an emergency contact at the screening visit in case we cannot reach them because they moved, are in a hospital, etc. The emergency contact is usually someone that does not live with them, or at least someone with a different phone number.

This process will be initiated when the subject has not shown up to a study visit. If no response is received from the subject within 60 days of missing the study visit, the subject will be withdrawn from the study and considered lost to follow-up.

**Drop outs/Treatment failures:** Dropouts may occur due to participant choice or physician recommendation for reasons such as adverse effects, poor compliance, etc.

If a subject is randomized but misses Orientation, the instructors may offer the subject an individual Orientation session. If the subject is unable to complete Orientation before Class #2 after being randomized, they will not be permitted to continue in the study.

As soon as a subject is determined to be Lost to Follow-up, Withdrawn or Completed, all data collection will cease after collecting reasons for participant-initiated withdrawal on the Attrition Survey. The date a subject is no longer considered part of the study will be documented in an End of Trial form.

**Attrition Information:** CONSORT guidelines require a reason for dropout for every subject, and whether the reason was due to an adverse event. The research coordinator will collect attrition information for each dropout from the study, and record the dropout date, subjects' responses to Yes/No questions about general reasons for attrition that do not reveal the subjects' group assignment, and whether the dropout is Subject-initiated or Investigator-initiated.

If it is a Subject-initiated dropout or a lost to follow-up, the subject will be e-mailed a link to a REDCap Participant-Completed Attrition Information Survey consisting of one open

ended question to elicit feedback about their experience in the study and learn more about their reasons for not continuing in the study. As subjects' responses could reveal group assignment, the research coordinator and other blinded study team members will be blinded to subjects' responses to this survey in REDCap.

Investigator-initiated withdrawals: A subject may also be withdrawn from the study and/or intervention by the investigator. In this case, the research coordinator will record the reasons why the investigator withdrew the subject from the study (See DSMP).

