Subjects will be given a Home A1CNow Self Check kit at baseline, or if they received a kit at screening they will be asked to bring the kit to their remote or in-person baseline visit. If the baseline study visit is conducted remotely, subjects will be mailed the Home A1cNow Self Check Kit. The research coordinator will review procedures and watch instructional videos with subjects, and assist the subjects in obtaining their hemoglobin A1C value from the kit. Subjects who complete their baseline study visit in the CRC will bring this kit home in case, for any reason, they are not able to return to the CRC for their 2 month and 6 month visit so that they will be able to collect their hemoglobin A1C results at home as this is the primary outcome for this study. If the 2 month and 6 month visits are being conducted at the CRC, the subjects will be asked to bring their Home A1CNow Self Check kit to the CRC and the kit will be used to collect their home hemoglobin A1c, in addition to the blood draw for hemoglobin A1c. The Home A1cNow Self Check Kit contains step by step instructions for subjects to reference for future testing.

If the subject opts-in to wearing an Actigraph device, the subject will be given an Actigraph device to wear around their waist for 7 days after the baseline visit. If the study visit is conducted remotely, the subject will be mailed the Actigraph device, with a stamped envelope to return after the required wear time.

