#### **7.2.4 Randomization and Study Intervention**

Randomization is a critical feature of a clinical trial because it prevents treatment-selection biases. Subjects will be randomized after obtaining their baseline measurements and within 1 week before the start of the study intervention (Orientation). It is anticipated that the amount

of time between randomization and the start of the study intervention (Orientation) will be no more than 1 week. There will be rolling enrollment. We will run a new cohort of MBSR and SME control classes approximately every 3 months. Subjects will only be randomized to a cohort if they indicate they are available for the intervention classes for that cohort.

Two hundred ninety (290) adults with uncontrolled diabetes will be randomized with equal allocation to one of two study groups for 6 months: (1) MBSR (n=145), or (2) SME control (n=145). Subjects will then undergo study visits again at 2 months (after Class #8/after the standard 8-week MBSR or SME program) and at 6 months (after Booster session #4/end of study), where the baseline procedures and measures will be repeated.

During the study, all subjects will continue to receive usual care from their physicians and will be advised not to change or discontinue any of their medications during the study unless directed to do so by their physician. As these subjects have uncontrolled diabetes, it is expected that they will be on medical treatment as prescribed by their physician, and they will be advised to follow-up with their physician every 3 months to ensure they are on optimal medical treatment. During the study, all subjects will be encouraged to continue their routine activities and they will be asked not to take part in any other formal stress reduction programs.

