### **Randomization Phone Call (by the SME instructor within 1-week before Orientation):**

At the end of the baseline visit, if a subject is deemed fully eligible for inclusion into the study, the research coordinator will inform the SME instructor, or other designated unblinded study team member, that the subject can be randomized during the week before Orientation. The SME instructor will disseminate the allocated randomized intervention to the subjects in their cohort, as the SME instructors are not blinded and they are not involved in the collection or analysis of study outcomes. During the Randomization phone call, the SME instructor will complete the following procedures to randomly assign the subjects in their cohort to one of two study groups (MBSR or SME) in REDCap:

- The SME instructor will call the subject in the week before the Orientation session.
  - If the SME instructor is unable to reach the subject for randomization, the SME instructor will email the subject to follow-up (See SME Instructor Email Template Randomization No Contact Made).
- The SME instructor will verify that the subject is still available for the study sessions. Subjects will be informed that they must attend the Orientation session to continue in the study. If they miss the Orientation session, and are unable to make up the Orientation before Class #2, they will not be able to continue in the study. If a subject thinks they will miss the Orientation, or if they think they will miss more than 2 classes during the first 8 weeks (including Class #1 to 8 and the Retreat), they will be encouraged to wait for another wave/cohort when they are able to make the time commitment. The SME instructor will not randomize any subjects who cannot commit, with reasonable certainty, to completing an Orientation session before Class #2, and at least 7 out of 9 classes during the first 8 weeks (including Class #1 to 8 and the Retreat).
- Upon confirming the subject's commitment to attendance and interest in participation, the SME instructor will select the randomization button in REDCap while they are still on the phone with the subject. Once the button is selected, the live feedback from REDCap will display the assigned group. In the same phone call (using a Randomization Script), the SME instructor will immediately inform the subject of the details of their group assignment, give them a brief pre-orientation of the program, and provide the subject with:
  - Welcome information

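### The window for the optional 'baseline' diet recalls straddles randomization, disclosure of the arm and Orientation, and a late baseline visit can do the same to the Actigraph week, so these baselines are not reliably pre-treatment

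*Combined protocol and SAP*

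**What the plan says.** The overview of visit windows in section 7.2.2 sets the relevant dates. On randomization: "Randomization will take place during the week before the Orientation session". On the first class: "Class #1 (the first class after Orientation) will start ~1 week after the Orientation session". On the recalls: "The time windows for capturing the optional 24-hour diet recall data are within 2 weeks before Class #1". The same recall window appears in the end-of-screening procedures in section 7.2.2 and in the dietary recall part of section 7.2.3, which assigns two recalls (one weekday, one weekend) to the baseline time point. Each recall covers the previous calendar day.

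Section 7.2.4 gives the intended order: "Subjects will be randomized after obtaining their baseline measurements and within 1 week before the start of the study intervention (Orientation"; the parenthesis identifies Orientation as the start of the intervention. Subjects learn their arm at once: "In the same phone call (using a Randomization Script), the SME instructor will immediately inform the subject of the details of their group assignment".

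For the accelerometer, section 7.2.3 says that "the subject will be given an Actigraph device to wear around their waist for 7 days after the baseline visit", and section 7.2.2 allows a wider range: "The time windows for capturing the optional Actigraph data are +/- 2 weeks of the baseline and 2-month study visits". The visit itself has an outer limit: "The baseline study visit will be scheduled within 6 weeks and 2 days (44 days) before the Orientation session". No minimum lead is given, except that the visit must precede randomization.

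Table 3 lists both measures as behavioral outcomes with a baseline mark. Section 8.3 includes behavioral data among the outcomes to be modelled as change from baseline, compared between arms.

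**The concern.** The recall window is tied to Class #1, while the order stated in section 7.2.4 is tied to randomization and Orientation. Nothing requires the recalls to be finished before the randomization call, so the stated order is not secured for this measure.

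The arms differ in exactly these behaviors. Section 7.2.4 describes nutrition and exercise content in SME, and mindful eating, walking and yoga in MBSR only. Subjects know their arm and diet is self-reported, so reported or actual intake could begin to differ between arms once the arm is known. If it does, a contrast in change from that baseline may remove part of an early effect. The measures at stake are the diet and activity outcomes under the behavioral part of Aim 2.

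**Working it through.** The plan gives no figure on this point to reproduce. The check is calendar arithmetic with day 0 = Orientation.

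**Inputs from the documents.** Randomization call R lies between day −7 and day 0. Class #1 is at about day 7. The recall window is the 14 days ending at Class #1. Intake is one day before the report.

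**Windows.** Report days: [7 − 14, 7] = [−7, 7]. Intake days: [−8, 6].

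**Share of the window after the call, for a given R (no assumption on spread of calls).**

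| R | report day, (7 − R)/14 | intake day, (6 − R)/14 |
|---|---|---|
| −7 | 100% | 93% |
| −3.5 | 75% | 68% |
| 0 | 50% | 43% |

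The R = 0 row is also the share after Orientation.

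**Averaging over subjects.** Assumption, not in the documents: R uniform on [−7, 0] and recall days uniform over the window. The mean of R is −3.5, so:
- report day: 10.5/14 = 75% after allocation, 7/14 = 50% after Orientation;
- intake day: 9.5/14 = 68% after allocation, 6/14 = 43% after Orientation.

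**Both recalls of a subject, by intake day, placed independently.**
- Both after allocation: E[(6 − R)²]/196, with 6 − R uniform on [6, 13]. (13³ − 6³)/(3 × 7) = 1981/21 = 94.3, and 94.3/196 = 48%.
- Both before: E[(R + 8)²]/196, with R + 8 uniform on [1, 8]. (8³ − 1³)/(3 × 7) = 511/21 = 24.3, and 24.3/196 = 12%.
- The remaining two in five subjects have one of each.

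By report day the same formulas give 58% both after and 8% both before.

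**Sensitivity to the approximate date of Class #1.** With Class #1 at day 5 to day 9, the share after allocation is 61% to 87% by report day and 54% to 82% by intake day. The share after Orientation is 36% to 64% and 29% to 57%.

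**Actigraph.** Let the baseline visit be b days before Orientation. Default wear ends on day −b + 7. It enters the randomization week if −b + 7 > −7, that is b < 14, and passes Orientation if b < 7. Using the full window, the last possible day is −b + 14, and the limits become b < 21 and b < 14. A visit 21 or more days before Orientation gives a wholly pre-randomization window. The documents give no distribution of visit days, so I attach no percentage.

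**The case against.** The strongest defense has four parts.

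- **Some recalls are clean.** The window opens about when the randomization week opens, so a subject randomized late in that week can complete one or both recalls first. A reader might infer that every baseline recall is post-randomization; the dates do not support that. This part stands.
- **The percentages rest on an assumed spread.** The protocol does not say when in the window the e-mails go out, and one recall must be a weekday and one a weekend day. This also stands, though the overlap itself needs no assumption.
- **No diet content is shown before Class #1.** All subjects get the same diet and activity handouts at baseline, the only Orientation content described is participant interviews, and assigned home practice starts after Class #1. A reader might infer that the randomization call tells SME subjects about nutrition teaching, but the script is not reproduced and the protocol mentions only assignment details and a brief pre-orientation. This weakens the mechanism without removing it: knowing the arm can still change behavior or reporting.
- **The stakes are limited.** Both measures are optional, and neither is named in Aim 2 or section 1.3 except through general references to behavioral measures. This stands.

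A reader might also infer that the analysis will adjust for a post-randomization covariate. Section 8.3 does not list diet or activity among its candidate covariates, and baseline enters the mixed model as a level of time, so only the change-from-baseline concern is tied to a planned analysis.

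**Conclusion.** The point holds in a limited form. As written, the plan lets the baseline diet recalls fall after allocation, disclosure and Orientation, contrary to its own stated order, and no other section cures this. Under an even spread most recalls do so: about 68% by intake day, or 54% to 82% as Class #1 moves from day 5 to day 9. Intake day is the better basis, because it is the day the data describe. For the Actigraph the problem is confined to subjects whose baseline visit falls late.

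The direction and size of any resulting bias cannot be derived from the documents. The consequence is confined to optional, secondary behavioral outcomes. The HbA1c analysis and the questionnaires completed at the baseline visit are not touched. This is an inexpensive improvement worth making, not a threat to the primary result.

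**What to change.** In the end-of-screening procedures and the window overview of section 7.2.2, and wherever the dietary recall part of section 7.2.3 repeats it, replace the baseline recall window tied to Class #1 with one that opens after the baseline visit and closes before the randomization call. The visit may be up to 44 days before Orientation, so there is usually room. Time the baseline Actigraph, whether handed over or mailed, so that wear ends before randomization.

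For cohorts already run, use the REDCap randomization time to flag each recall (by intake day) and each wear day as before or after allocation. Report a sensitivity analysis restricted to pre-randomization baseline data. Discarding the rest outright would be out of proportion: under the even-spread assumption it would remove about two thirds of baseline recalls.

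The cost is a wording change and earlier e-mails and device dates, with no added visit or measurement. Subjects with a late baseline visit may supply fewer recalls or wear days, and may lack time for both a weekday and a weekend recall. The restricted analysis of past cohorts will be small: only about 12% of subjects would have both recalls before allocation, and about 1 − 0.48 = 52% at least one.

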Missed 2-month and 6-month (in-person or remote) study visits: If the subject misses their 2-month or 6-month study visit, and has a lab result (e.g. lab hemoglobin A1c) outside of the study, the lab result (e.g. lab hemoglobin A1c) will be recorded as the study visit lab result (e.g. lab hemoglobin A1c) after verifying the result in outside records or the EMR.

All subjects will be given the same general written guidelines on diet and exercise at the baseline visit, which will consist of two handouts downloaded from the American Diabetes Association Patient Education Library: (1) “Plan Your Portions” Diabetes Placemat and (2) “The Diabetes Advisor - Physical Activity.” All subjects will also be given handouts on Hyperglycemia and Hypoglycemia, as well as Glucometer Best Practices and Blood Glucose Meter Correlation, at the baseline visit. This will be the only information that will be the same across both groups. The MBSR group will not receive any additional health education other than these handouts.

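### A subject who misses the 2-month visit and stays silent for 60 days is closed out before the 6-month window opens, so month-6 HbA1c, the primary endpoint, is never sought although consent was not withdrawn

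*Combined protocol and SAP*

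**What the plan says.** Section 7.2.2 sets the visit windows: "The 2-month study visit will be scheduled within the 4 weeks immediately after Class #8" and "The 6-month study visit will be scheduled within the 4 weeks immediately after Booster session #4". Section 7.2.4 places the four boosters in Months 3 to 6. Section 1.2 makes HbA1c at the 6-month visit the primary endpoint.

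The lost-to-follow-up rule is in the same Section 7.2.2. Its trigger is any visit: "This process will be initiated when the subject has not shown up to a study visit". The contact steps are that "the research coordinator will call and e-mail the subject once a week for 3 weeks", followed by three attempts to reach an emergency contact if one was given. The end point is: "If no response is received from the subject within 60 days of missing the study visit, the subject will be withdrawn from the study". The consequence is: "As soon as a subject is determined to be Lost to Follow-up, Withdrawn or Completed, all data collection will cease", with only the attrition survey excepted.

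A subject who misses the 2-month visit has one protection: "if the subject confirms that they are willing to come in for the final 6-month study visit, the subject will not be withdrawn". It requires the subject to answer.

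Three other places point the other way:
- Table 3, footnote a, opens a rule with "If the subject misses their 2-month or 6-month study visit, and has a lab result (e.g. lab hemoglobin A1c) outside of the study" and has the verified outside value recorded as the study visit result.
- Section 7.2.7 repeats this capture of outside HbA1c for a missed 6-month visit.
- Section 9.3, and Section IV.E of the Data and Safety Monitoring Plan, state that every subject is followed to 6 months.

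**The concern.** The 2-month visit is not the primary time point, yet missing it and then staying silent ends a subject's participation. As the rule is written, nobody tries again at 6 months, offers a remote visit or home kit, or looks for an outside HbA1c. Silence leads to the same stop on data collection as a decision to withdraw.

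At stake is avoidable missing primary data among the least engaged subjects, where missing at random is hardest to defend. Section 8.3 promises intention-to-treat inclusion of every randomized participant's data, but for these subjects there would be no month-6 value to include. The mixed model would lean on the subjects who attended. Section 8.3 says only that methods for differential dropout will be considered, and it commits to no specific sensitivity analysis. Preventing the loss is therefore the main safeguard.

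**Working it through.** **The plan's own sample size.** Inputs from Section 8.2: difference 0.5, SD 0.9, two-sided 0.05, power 80%, class size 18, ICC 0.08, dropout 15%.
- Per arm before inflation: 2 × (0.9 × (1.960 + 0.842) / 0.5)² = 50.9, so 51. The t-based figure is 52.
- Design effect: 1 + (18 − 1) × 0.08 = 2.36.
- Normal approximation: 51 × 2.36 = 120.4, so 121; 121 / 0.85 = 142.4, so 143 per arm, or 286 in total.
- t-based: 52 × 2.36 = 122.7, so 123; 123 / 0.85 = 144.7, so 145 per arm, or 290 in total.

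The stated 290 reproduces, and it already allows for about 44 dropouts (0.15 × 290 = 43.5).

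**The calendar.** Take Orientation as day 0. Class #1 is about a week later (day 7) and Class #8 is seven weeks after that (day 56). The 2-month window runs from day 56 to day 84. Adding 60 days puts withdrawal on day 116 if the visit is missed on the first day of the window, and on day 144 if the miss is dated from window close. Section 7.2.2 defines the miss relative to the window, so day 144 is the more natural date.

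The documents give no calendar day for Booster #4, so several readings are shown. The gap is the Booster #4 day minus 144.

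| Assumed timing of Booster #4 | Day | Gap (days) |
|---|---|---|
| Class #8 + 4 months of 30 days (56 + 120) | 176 | 32 |
| Class #8 + 4 months of 28 days (56 + 112) | 168 | 24 |
| First day of Month 6 from Class #1, 30-day months (7 + 150) | 157 | 13 |
| First day of Month 6 from Class #1, 28-day months (7 + 140) | 147 | 3 |
| First day of Month 6 from Orientation, 30-day months | 150 | 6 |
| First day of Month 6 from Orientation, 28-day months | 140 | −4 |

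On the first two readings, a miss dated from day 56 widens the gap to as much as 176 − 116 = 60 days. Only the last reading, combined with a miss dated from window close, lets the 6-month window open before withdrawal, and then by 4 of its 28 days.

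**What more loss would cost in power.** The documents do not say how many subjects are affected, so the loss rates here are assumptions. Power is Φ(0.5 / (0.9 × √(2/n)) − 1.96), with n = 145 × (1 − loss) / 2.36.
- 15% loss: 81.0%
- 18%: 79.6%
- 20%: 78.7%
- 25%: 76.0%
- 30%: 73.1%

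If the class size in the design effect shrinks with the losses, power is 84.6% at 15% and 81.3% at 30%.

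**Illustration of what could be recovered (all shares assumed).** Suppose one-third to two-thirds of the 44 dropouts arise this way (15 to 29) and 25% to 50% of them would yield a month-6 value. That is about 4 to 15 values. Suppose further that these subjects do 0.5 points worse than modelled and that their share differs by 5 to 10 percentage points between arms. The contrast then shifts by 0.5 × 0.05 to 0.5 × 0.10 = 0.025 to 0.05. Only the recovered part is avoidable: 0.025 × 0.25 to 0.05 × 0.50 = about 0.006 to 0.025, or 1% to 5% of the 0.5 target. A 10-point imbalance is 14.5 of 145 subjects, so with only 15 affected nearly all would have to be in one arm.

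**The case against.** The strongest defence is that the rule catches only people silent on every channel, and that 290 already carries a 15% allowance, with up to 320 randomizations permitted in Section 8.1. Much of this stands. Several stronger readings are tempting, and the documents do not support them.

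- *Subjects still attending boosters or answering daily surveys are withdrawn anyway.* The text does not say so. Section 7.2.4 gives the SME instructor the role of main contact, and Sections 7.2.3 and 7.2.4 provide reminder calls before the monthly boosters. Whether any of this counts as a response is left undefined.
- *Affected subjects enter the model with baseline only.* Not established. An outside HbA1c for the missed 2-month visit may be recorded during the 60 days before withdrawal.
- *The provisions flatly contradict each other.* For the 2-month value they can work in sequence, with records searched until the subject is declared lost. For month 6 that does not help, because collection has stopped before the visit falls due.
- *The sample size fails.* It does not. The power effect is modest, and some of the loss is already budgeted.
- *Records could certainly be searched after loss to follow-up.* This depends on consent and authorization text that was not available for review. A home-kit result also needs the subject to respond, since the coordinator assists with the reading.
- *The stop on collection should apply only to consent withdrawals.* That would also lift it for completed subjects and investigator withdrawals, for which there is no argument here.

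**Conclusion.** The concern holds as a timing and consistency problem. Followed as written, Section 7.2.2 withdraws a silent subject who missed the 2-month visit no later than about day 144 after Orientation. That is 24 to 60 days before the 6-month window if Booster #4 falls four months after Class #8, and it is earlier than the window on every reading examined except one extreme one. Month-6 HbA1c is then never sought, although consent was not withdrawn. Table 3 footnote a, Section 7.2.7 and Section 9.3 do not fit with this outcome and must be reconciled with Section 7.2.2.

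The number of subjects affected cannot be derived from the documents. The recovery and bias figures above rest on assumed shares, and the conclusion does not depend on them. The case rests on avoidable, probably informative missing primary data and on the internal mismatch. This is a cheap improvement worth making.

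**What to change.** Amend Section 7.2.2 as follows:

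1. A missed 2-month visit without a response does not by itself lead to withdrawal. The subject stays active with missing 2-month data and is approached again for the 6-month visit, in person, remotely or with the home kit.
2. Loss to follow-up is declared only after the 6-month window has closed and the existing contact steps have failed.
3. For lost-to-follow-up subjects only, the month-6 outside HbA1c capture in Table 3 footnote a and Section 7.2.7 is exempt from the stop on data collection, as far as the signed consent and authorization allow. The stop stays unchanged for completed subjects, consent withdrawals and investigator withdrawals.
4. Any contact with study staff or instructors counts as a response, and the text says whether a daily survey reply does. The SME instructor can pass on the bare fact of contact through the channel already set up in Section 7.2.4, so blinding is kept.

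The cost is amendment wording and a few extra calls, kits and record look-ups. No new procedure is needed. The downside is that some subjects stay in active status longer.
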